11.1 OPERATIVE MANAGEMENT OF MEDICAL WRITING ASPECTS

The results of this study will be published or presented at scientific meetings. Participant Investigator agrees to submit all manuscripts or abstracts to BITSPA prior to submission. This allows the sponsor to protect proprietary information and to provide comments based on information from other studies that may not yet be available to the Investigator.

In accordance with standard editorial and ethical practice, BITSPA will generally support publication of multicenter studies only in their entirety and not as individual center data. In this case, the Study Advisory Board will be designated.

The investigator has to provide the sponsor all data derived by the investigator from the study. During the study, only the sponsor may make study information available to other study investigators or to regulatory agencies, except as required by law or regulation. Except as otherwise allowable in the clinical study site agreement, any public disclosure (including publicly accessible websites) related to the protocol or study results, other than study recruitment materials, is the sole responsibility of the sponsor.

Manuscript authorship for any peer-reviewed publication will appropriately reflect contributions to the production and review of the document. All publications and presentations must be prepared in accordance with this section and the Study Site Agreement, which has to be written consequently.

BITSPA also adheres to any additional standards concerning authorship required by a specific journal or congress to which the publication is submitted. The responsible individuals at BISPA apply, at a minimum, the following criteria to determine who is named as an author on a publication:

- Substantial contributions to the concept and design, acquisition of data, or analysis and interpretation of data
- Drafting of the publication or revising it critically for important intellectual content
- Final approval of the version to be published
- Agreement to be accountable for all aspects of the work in ensuring that questions related to the accuracy or integrity of any part of the work are appropriately investigated and resolved.

Authorship criteria and obligations apply equally to BITSPA employees and non-employees. Each listed author must have participated in the work enough to take public responsibility for appropriate portions of the content.

Individuals contributing to the publication but not meeting authorship criteria may be appropriately acknowledged in the publication.

11.2 GHOSTWRITING AND GUEST/GHOST AUTHORSHIP

Ghostwriting, guest authorship, and ghost authorship are strictly prohibited. The contribution of a writer, which, when performed under the direction of the author(s), is considered a form of specialized, technical assistance, is acknowledged in the earliest draft in which the writer is involved.

11.3 DETERMINING ORDER OF AUTHORSHIP

Author order is determined by mutual agreement at the earliest possible time, with due consideration to overall contributions to the study, to the publication, or to scientific knowledge of the subject matter.

12.2 UNPUBLISHED REFERENCES

Not applicable.

ANNEX 1. LIST OF STAND-ALONE DOCUMENTS

| Number | Document Reference Number | Date | Title |
|--------|---------------------------|------------------------|---|
| 1 | 1 | 26th June, 2015 | List of BITSPA allocated Team |
| 2 | 2 | 26th June, 2015 | List of all main Principal Investigators participant to the study |
| 3 | 3 | 26th June, 2015 | List of Advisory Board members |
| 4 | 4 | 26th June, 2015 | List of allocated Team |
| 5 | 5 | 26th June, 2015 | Assessment of IPF with HRCT or/and surgical lung biopsy |
| 6 | 6 | 26th June, 2015 | Approval/signature page |

ANNEX 2. ENCEPP CHECKLIST FOR STUDY PROTOCOLS

A copy of the ENCePP Checklist for Study protocols (version 2) available at website: encepp.eu/standards_and_guidances/index.html completed and signed by the main authors of the study protocol should be included in Annex 2.

The checklist will facilitate the review of the protocol and evaluation of whether investigators have considered important methodological aspects.

In question 9.5 of the Checklist, Revision 1:

*“Study start” means “Start of data collection”
“Study progress” means “Progress report(s)”
“Study completion” means “End of data collection”
“Reporting” means “Final report of the study results”*

ANNEX 3. ADDITIONAL INFORMATION

None.

ALAT	Latin American Thoracic Association
ATS	American Thoracic Society
BAL	BronchoAlveolar Lavage
BITSPA	Boehringer Ingelheim Italy S.p.A.
BMI	Body Mass Index
BS	Biostatistician
CI	Confidence Interval
CDM	Clinical Data Manager
CNS	Central Nervous System
CRF	Case Report Form
CTCAE	Common Terminology Criteria for Adverse Events
DLCO	Diffusion Lung Capacity for carbon monoxide
eCRF	Electronic Case Report Form
EQ-5D-5L	EuroQol 5-dimension 5-level
ERS	European Respiratory Society
FVC	Forced vital capacity
FEV1	Forced expiratory volume in the 1st second
HRCT	High Resolution chest Computer Tomography
HRQoL	Health Related Quality of Life
ILD	Interstitial Lung Disease
INHS	Italian National Health Service
IPF	Idiopathic Pulmonary Fibrosis
JRS	Japanese Respiratory Society
LTOT	Long-Term Oxygen Therapy
LTx	Lung Transplantation
Max	Maximum
MAH	Market Authorization Holder
MedDRA	Medical Dictionary for Drug Regulatory Activities
Min	Minimum
MMF	Mycophenolate MoFetil
N	Number of observations
NIS	Non-interventional Study
p.o.	per os (oral)
PRO	Patient Related Outcomes
q.d.	queaque die (once a day)
QoL	Quality of Life
SAE	Serious Adverse Event
SAP	Statistical Analysis Plan
s.c.	subcutaneous
SGRQ	St. George's Hospital Respiratory Questionnaire
SD	Standard Deviation
t.i.d.	ter in die (3 times a day)
VC	Vital Capacity
TLC	Total Lung Capacity
UIP	Usual Interstitial Pneumonia

1 STATISTICAL ANALYSIS PLAN OBJECTIVES

The FIBRONET study is a multi-center, non-interventional (observational) prospective cohort study based mainly on newly collected data. A total of 200 consecutive patients will be enrolled in approximately 18 months (from the first patient enrolled). Patients will be followed-up for 1 year, with 3 intermediate evaluations after 3 (± 1), 6 (± 1) and 9 (± 1) months since baseline (which is compatible with current clinical practice in Italy for IPF patients management).

The present Statistical Analysis Plan has been designed considering the following input documents: the Study Protocol v.1.0 26/06/2015 and the electronic case report form v. 1.1.1 30/11/2015.

This SAP is aimed at evaluating the following study objectives:

Primary objective:

1. In a sample of IPF diagnosed patients to describe the clinical course during 12 months of observation, in terms of:
 - IPF symptoms
 - lung function (VC, FVC, FEV1, TLC, DLCO, pO₂, pCO₂; SaO₂, PaO₂ and PaCO₂ at rest)
 - exercise tolerance (6-minute walk distance test)

Secondary objectives:

1. Description of characteristics of IPF patients at enrollment in terms of:
 - key (socio-) demographic data
 - IPF risk factors, comorbidities
 - IPF disease severity and manifestation (including lung function, cardiopulmonary exercise testing and/or exercise capacity if available, laboratory values)
 - Methods used for IPF diagnosis
 - IPF treatment modalities (detailed information on prescribed drugs and dose; non-pharmacological treatment; lung transplantation)
2. To describe the frequency of exacerbations during 12 months of observation.
3. To describe HRQoL variation, measured with SGRQ, EuroQol (EQ) 5-dimension 5-level (EQ-5D-5L) descriptive system and EQ VAS, during 12 months of observation.
4. To describe health care sector-related costs from diagnosis up to the end of 12-month follow-up according to the Italian National Health Service (INHS) point of view.

The ongoing (pharmacological and non-pharmacological) therapies at each follow up
will be described too.

In this document the eCRF fields are indicated as follows: "label of the field" [[name of the eCRF form.name of the variable in the dataset](#)].

2 DEFINITION OF EVALUABLE PATIENTS

All enrolled patients fulfilling the following criteria will be considered evaluable for the evaluation of FIBRONET primary study objective:

*It will be recalculated considering for all patients day=01.

¹ The number of patients evaluable for analyses will be previously shared with sponsor for approval before first release of statistical report.

4. Patient with further follow-up possible with enrolling investigator during planned study period
 - Question "4. Patient with further follow-up possible with enrolling investigator during planned study period" = "Yes" [\[F01_INC_EXC_CRITERIA.CI_4\]](#)
AND
 - 4. Patient with further follow-up possible with enrolling investigator during planned study period [\[F27_PROTOCOL_DEVIATION_FORM.PD_CI_4\]](#) not checked
5. Patient capable of discernment and able to read or write in Italian language
 - Question "5. Patient capable of discernment and able to read or write in Italian language" = "Yes" [\[F01_INC_EXC_CRITERIA.CI_5\]](#)
AND
 - 5. Patients capable of discernment and able to read or write in Italian language. [\[F27_PROTOCOL_DEVIATION_FORM.PD_CI_5\]](#) not checked
6. Patient not included in clinical trials or other IPF/ILD registries
 - Question "6. Inclusion in clinical trials or other IPF/ILD registries" = "No" [\[F01_INC_EXC_CRITERIA.EC_1\]](#)
AND
 - 1. Inclusion in clinical trials or other IPF/ILD registries [\[F27_PROTOCOL_DEVIATION_FORM.PD_EC_1\]](#) not checked
7. Patient without lung transplantation expected within the next 6 months
 - Question "7. Lung transplantation expected within the next 6 months" = "No" [\[F01_INC_EXC_CRITERIA.EC_2\]](#)
AND
 - 2. Lung transplantation expected within the next 6 months [\[F27_PROTOCOL_DEVIATION_FORM.PD_EC_2\]](#) not checked
8. Female patient not pregnant at enrollment or breast feeding
 - Question "8. Pregnancy or breast feeding" = "No" [\[F01_INC_EXC_CRITERIA.EC_3\]](#)
AND
 - 3. Pregnancy or breast feeding [\[F27_PROTOCOL_DEVIATION_FORM.PD_EC_3\]](#) not checked
9. Male and female patients
 - Gender at enrollment visit [\[_PatientInfo.Gender\]](#) not missing
10. Available evaluation of at least one of the following at enrollment:
 - IPF symptoms
 - IPF symptoms at study visit? [\[F06_IPF_SYMPTOMS.SYM_IPF_symptoms_YN\]](#)= Yes and at least one symptom [\[F06_IPF_SYMPTOMS.SYM_IPF_symptoms, SYM_IPF_symptoms_other\]](#) not missing OR IPF symptoms at study visit? = No OR mMRC dyspnea score [\[F15_MMRC.MMRC\]](#) not missing.
 - Lung function (VC, FVC, FEV1, TLC, DLCO, pO2, pCO2; SaO2, PaO2 and PaCO2 at rest)
 - [\[F07_LUNG_FUNCTION_ASS.LU_Spirometry_YN\]](#)=Yes and at least one parameter [\[F07_LUNG_FUNCTION_ASS.LU_FEV1--LU_saO2_Num\]](#) not missing.
 - [\[F07_LUNG_FUNCTION_ASS.LU_Emogas_YN\]](#)=Yes and at least one parameter [\[F07_LUNG_FUNCTION_ASS.LU_Po2_Num, LU_PaO2_Num, LU_PCO2_Num, LU_PaCO2_Num\]](#) not missing.
 - Exercise tolerance (6-minute walk distance test)
 - [\[F07_LUNG_FUNCTION_ASS.LU_6_Minute_YN\]](#)=Yes and 6-minute walked distance (m) [\[F07_LUNG_FUNCTION_ASS.LU_6_minute_distance_Num\]](#) not missing.

Patient who performed V2 (3-months), V3 (6-months), V4 (9-months), V5 (12-months) follow up visit

At each follow up visit they will be defined as patients satisfying the following criteria:

1. Patients evaluable at enrollment (i.e., responding to criteria of par 2.1 Patients evaluable at enrollment)

2. Data collected at x-month follow-up = "Yes" **[F16_PATIENT_DISPOSITION, 3 month f-up.PD_1; 6 month f-up.PD_1; 9 month f-up.PD_1; 12 month f-up.PD_1]**
where x=3-, 6-, 9-, 12-
3. Follow-up performed at $x \pm 1.5$ months from enrollment (where x=3-, 6-, 9-, 12-)
 - (Date of follow up visit (dd/mmm/yyyy) **[F16_PATIENT_DISPOSITION, 3 month f-up.PD_2; 6 month f-up.PD_2; 9 month f-up.PD_2; 12 month f-up.PD_2]**– Date of enrolment visit (dd/mm/yyyy) **[_PatientInfo. Date_enrollment]**) $/30.4375 \geq 1.5$ (or 4.5 or 7.5 or 10.5))
AND
 - (Date of follow up visit (dd/mmm/yyyy) **[F16_PATIENT_DISPOSITION, 3 month f-up.PD_2]**– Date of enrolment visit (dd/mm/yyyy) **[_PatientInfo. Date_enrollment]**) $/30.4375 \leq 4.5$ (or 7.5 or 10.5 or 13.5))
4. With available IPF symptoms evaluation at baseline and at $x \pm 1.5$ months from enrollment (where x=3-, 6-, 9-, 12-)
 - (IPF symptoms at baseline ? **[F06_IPF_SYMPTOMS.SYM_IPF_symptoms_YN]**=No OR (IPF symptoms at baseline?=Yes AND at least one symptom **[F06_IPF_SYMPTOMS.SYM_IPF_symptoms, SYM_IPF_symptoms_other]** not missing))
AND
 - (IPF symptoms at x-month follow up? **[F06_IPF_SYMPTOMS.SYM_IPF_symptoms_YN]**=No OR (IPF symptoms at x-month follow up?=Yes AND at least one symptom **[F06_IPF_SYMPTOMS.SYM_IPF_symptoms, SYM_IPF_symptoms_other]** not missing))
where x=3-, 6-, 9-, 12-

IPF symptoms

For patients with *if other symptom, specify* **[F06_IPF_SYMPTOMS.SYM_IPF_symptoms, SYM_IPF_symptoms_other]** =EXERTIONAL DYSPNEA or DISABLING DYSPNEA the field will be considered as DYSPNEA.

Incident IPF symptom at x-month follow up

IPF symptom absent at enrollment visit and present at x-month follow-up visit) **[F06_IPF_SYMPTOMS.SYM_IPF_symptoms]**
Where x=3-, 6-, 9-, 12-

Patients with incident IPF symptom at x-month follow up

Patients with incident IPF symptom (according to previous definition) over total number of patients without symptom at baseline.
Where x=3-, 6-, 9-, 12-

Remitted IPF symptom at x-month follow up

IPF symptom present at enrollment visit and absent at x-month follow-up visit) **[F06_IPF_SYMPTOMS.SYM_IPF_symptoms]**
Where x=3-, 6-, 9-, 12-

Patients with remitted IPF symptom at x-month follow up

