8. RESEARCH METHODS

8.1 STUDY DESIGN

This is an observational, multicenter prospective cohort study based on newly collected data, involving 20 Italian Pulmonary Centers highly experienced in the disease management of IPF.

The enrolment period will last 18 months. During this period, about 200 consecutive patients will be included in agreement with the inclusion/exclusion criteria. Patients will be followed up for 1 year, with 3 intermediate evaluations after 3 (+/-1), 6 (+/-1) and 9 (+/-1) months from baseline (such visits are referred as being the current clinical practice in Italy for IPF patients management).

No treatment will be administered to the patients on the protocol basis, since this is an observational study and the assessment and treatment of the enrolled patients is based only on the investigators' clinical routine practice.

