8.3 VARIABLES

This is a non-interventional study and does not impose a therapy protocol, diagnostic/therapeutic procedure, or a visit schedule. Patients will be treated according to the local prescribing information and routine medical practice in terms of visit frequency and types of assessments performed and only these data will be collected as part of the study. The treating physician is asked to complete if possible at every patient visit the appropriate CRF.

Primary endpoints will be: symptoms, lung function (VC, FVC, FEV1, TLC, DLCO, pO₂, pCO₂; SaO₂, PaO₂ and PaCO₂ at rest), exercise tolerance (6-minute walked distance test) both at baseline and at follow-up visits.

Secondary endpoints will be: (socio-) demographic data, IPF risk factors, comorbidities, IPF disease severity and manifestation (including lung function, cardiopulmonary exercise testing and/or exercise capacity if available, laboratory values), methods used for IPF diagnosis, IPF treatment modalities (prescribed drugs and dose; non-pharmacological treatment; lung transplantation); exacerbations SGRQ and EuroQol (EQ) 5-dimension 5-level (EQ-5D-5L). Finally health care resources will be collected

Below is the recommended assessment schedule that most likely mirrors the patterns of routine clinical care of most patients.

| Study Visits | Visit 1 | Visit 2 | Visit 3 | Visit 4 | Visit 5 |
|---|----------|-------------|-------------|-------------|-------------|
| | Baseline | Follow-up 1 | Follow-up 2 | Follow-up 3 | Follow-up 4 |
| Months | 0 | 3 (+/-1) | 6 (+/- 1) | 9 (+/- 1) | 12 (+/- 1) |
| Eligibility criteria Inclusion and exclusion criteria, Informed consent and privacy form | X | | | | |
| Baseline information (Socio-)demographic variables: age, gender, race, body mass index, geographic location, educational degree, marital status, housing situation and employment status | X | | | | |
| Potential IPF risk factors Cigarette smoking (including pack/years), environmental exposure, drug exposure, family history, other | X | X | X | X | X |
| Comorbidities Atherothrombotic disease including coronary heart disease, previous myocardial infarction, cerebrovascular disease, peripheral arterial disease, gastroesophageal reflux disease, pulmonary hypertension, emphysema, lung cancer, renal insufficiency | X | X | X | X | X |

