4.4 Primary objective: Clinical course of IPF during observation**Table 13. IPF symptoms**

The table will provide at enrollment and at V2, V3, V4, V5:

- Frequency distribution of patients with at least one IPF symptom [\[F06_IPF_SYMPTOMS.SYM_IPF_symptoms_YN\]](#)
- Frequency distribution of IPF symptoms [\[F06_IPF_SYMPTOMS.SYM_IPF_symptoms\]](#)

Descriptives will be computed out of the total number of patients who performed the specific visit.

Table 20. Lung Function Assessments – Spirometry at each study visit and variation during observation period

The table will provide at enrollment, V2, V3, V4, V5 main descriptive statistics (mean, median, standard deviation, quartiles, min, max) of:

- FEV1 (L) [\[F07_LUNG_FUNCTION_ASS.LU_FEV1\]](#)
- FEV1 of the predicted (%) [\[F07_LUNG_FUNCTION_ASS.LU_FEV1_predicted\]](#)
- FVC (L) [\[F07_LUNG_FUNCTION_ASS.LU_FVC\]](#)
- FVC of the predicted (%)
- FEV1/FVC (%) [\[F07_LUNG_FUNCTION_ASS.LU_FEV1_FVC\]](#)

- Total lung capacity (L) [\[F07_LUNG_FUNCTION_ASS.LU_TLC_Num\]](#)
- DLCO [\[F07_LUNG_FUNCTION_ASS.LU_DLCO_Num\]](#), along with the respective DLCO unit [\[F07_LUNG_FUNCTION_ASS.LU_DLCO_unit\]](#).
- DLCO of the predicted (%) [\[F07_LUNG_FUNCTION_ASS.LU_DLCO_Predicted_Num\]](#)
- SaO2 (%) [\[F07_LUNG_FUNCTION_ASS.LU_SAO2_Num\]](#)
- change at each follow-up visit vs baseline of FEV1 (L)
- change at each follow-up visit vs baseline of FEV1 of the predicted (%)
- change at each follow-up visit vs baseline of FVC (L)
- (absolute and relative) change at each follow-up visit vs baseline of FVC of the predicted (%)
- change at each follow-up visit vs baseline of FEV1/FVC (%)

- change at each follow-up visit vs baseline of Total lung capacity (L)
- change at each follow-up visit vs baseline of DLCO, along with the respective DLCO unit
- change at each follow-up visit vs baseline of DLCO of the predicted (%)
- change at each follow-up visit vs baseline of SaO2 (%)

Evaluable patients at the specific visit with spirometry performed [\[F07_LUNG_FUNCTION_ASS.LU_spirometry_YN\]](#) at study visit or in the previous 3 months will be considered.

Table 21. Lung Function Assessments – Emogas analysis at each study visit and variation during observation period

The table will provide at enrollment, V2, V3, V4, V5 the main descriptive statistics (mean, median, standard deviation, quartiles, min, max) of:

- PO2 (mmHg) [\[F07_LUNG_FUNCTION_ASS.LU_PO2_Num\]](#)
- PaO2 (mmHg) [\[F07_LUNG_FUNCTION_ASS.LU_PaO2_Num\]](#)

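### SAP section 3 counts a follow-up visit only if its month-named form and its date window agree, so a record dated in a neighbouring window is used nowhere in the by-visit tables; the printed upper limit also names the wrong date field

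*SAP*

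**What the plan says.** SAP section 3 (Computed variables) defines the patients who performed V2, V3, V4 and V5 by four conditions, all of which must hold: evaluable at enrolment; the form for that month marked as collected; "Follow-up performed at $x \pm 1.5$ months from enrollment (where x=3-, 6-, 9-, 12"; and symptom data available at baseline and at that visit.

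The third condition is then written as two inequalities. The lower-limit line lists the 3-, 6-, 9- and 12-month visit dates in parallel with their limits ("30.4375 \geq 1.5$ (or 4.5 or 7.5 or 10.5"). The upper-limit line gives four limits ("30.4375 \leq 4.5$ (or 7.5 or 10.5 or 13.5") but only one date field, "F16_PATIENT_DISPOSITION, 3 month f-up.PD_2".

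The definition feeds the by-visit tables. For Table 13, "Descriptives will be computed out of the total number of patients who performed the specific visit". Tables 26-27, 35-37, 39-41 and 46-48 have matching denominators. Tables 20-22 use evaluable patients at the specific visit, which is most naturally read as the same set.

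On timing, Protocol section 8.1 describes a one-year follow-up "with 3 intermediate evaluations after 3 (+/-1), 6 (+/-1) and 9 (+/-1) months from baseline", and the section 8.3 table gives ±1 month for month 12 as well. Section 8.3 also states: "This is a non-interventional study and does not impose a therapy protocol, diagnostic/therapeutic procedure, or a visit schedule".

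**The concern.** The windows cover follow-up from 1.5 to 13.5 months without a gap, so a record that misses its own window will often lie inside a neighbouring one. Each record is tested only against the window of its own form. If it fails, it is not offered to the window where its date falls, even when that window has no other record for the patient.

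The data lost would already have been collected, and they bear on the primary objective. The output would not explain the loss. Table 1 would show fewer patients at a visit but not why, Table 3 covers withdrawals only, and Table 4 describes timing only among patients who passed. The 20% to 40% drop-out assumed in Protocol section 8.5 rests on mortality and natural drop-out, so window exclusions would come on top of it.

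**Working it through.** **1. The plan's own figures.** Protocol section 8.5: 200 × (1 − 0.40) = 120 and 200 × (1 − 0.20) = 160 evaluable at 12 months. For FVC (mean 2.37 L, SD 0.73 L), 2.37 ± 1.96 × 0.73/√120 gives 2.24 to 2.50, and with √160 it gives 2.26 to 2.48, as printed. The documents give no figure for visits lost to the window rule.

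**2. Windows in days** (SAP divisor 30.4375):

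| Visit | Limits, months | Limits, days | Whole days |
|---|---|---|---|
| 3-month | 1.5-4.5 | 45.66-136.97 | 46-136 |
| 6-month | 4.5-7.5 | 136.97-228.28 | 137-228 |
| 9-month | 7.5-10.5 | 228.28-319.59 | 229-319 |
| 12-month | 10.5-13.5 | 319.59-410.91 | 320-410 |

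There is no gap and no overlap, and no whole day falls on a limit.

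**3. Two readings of the third condition.**

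| Form and date | Window of the date | Rule as worded | Upper limit as printed |
|---|---|---|---|
| 3-month form, month 5 | 6-month | discarded | discarded |
| 6-month form, month 8 | 9-month | discarded | kept as month 6 |
| 9-month form, month 7 | 6-month | discarded | discarded |
| 9-month form, month 11 | 12-month | discarded | kept as month 9 |
| 12-month form, month 10 | 9-month | discarded | discarded |
| 12-month form, month 14 | none | discarded | kept as month 12 |

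The right-hand column assumes a 3-month visit date that itself meets the limit. As printed, a late 6-, 9- or 12-month form is never tested on its own date. A patient with no 3-month visit date has nothing to test, and the SAP does not say how the condition then resolves.

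**4. Size under the rule as worded.** Visit timing has to be assumed. All four visits are taken as made; the simulations compare the share of patients with a usable value when form and date must agree with the share when date alone decides.

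*Independent Normal deviations around months 3, 6, 9 and 12, at month 12:*

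| SD, months | Form and date | Date alone | Gain on 160 |
|---|---|---|---|
| 0.5 | 99.7% | 99.7% | about 0 |
| 0.75 | 95.5% | 95.6% | 160 × 0.001 ≈ 0.2 |
| 1.0 | 86.7% | 87.6% | 160 × 0.009 ≈ 1.4 |

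*Cumulative drift: each gap between visits Normal with mean 3 months:*

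| Gap SD, months | Month | Form and date | Date alone | Gain on 160 |
|---|---|---|---|---|
| 0.5 | 12 | 86.7% | 89.7% | 160 × 0.030 = 4.8 |
| 0.75 | 12 | 68.4% | 77.7% | 160 × 0.093 = 14.9 |
| 0.5 | 9 | 91.7% | 95.8% | 160 × 0.041 = 6.6 |
| 0.75 | 9 | 75.3% | 90.0% | 160 × 0.147 = 23.5 |

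Under drift the deviations add up, so the SD at the fourth visit is √4 = 2 times the gap SD. That is why the two models differ so much.

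**5. Precision.** Even if 30% were lost from 120, leaving 84, the FVC half-width is 1.96 × 0.73/√84 = 0.156 L, and 0.156/2.37 = 6.6%, well below the plan's 30% relative-error mark. Any harm would come from which patients are missing, not from wider intervals.

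**The case against.** Four points stand against making much of this.

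- **The window is generous.** At ±1.5 months it is wider than the protocol's ±1, so under the rule as worded every visit inside the protocol window passes the date test. Only visits more than half a month beyond it are at risk. The protocol also calls its schedule recommended and says it reflects Italian practice.
- **The forms are named by month.** A reader might infer that a centre seeing patients at months 4, 8 and 12 would file these on the 3-, 6- and 9-month forms and lose the month-12 assessment. The documents do not support that. With month-named forms the natural choice is the 3-, 9- and 12-month forms, and all three visits then pass.
- **The visits are anchored to baseline.** The protocol's wording fits independent deviations better than cumulative drift, so the small gain cannot be dismissed. A reader might also infer that labels are bound to drift and that the loss is known to be selective. No timing data are given, so selective loss is a possibility only.
- **The reach is limited.** Exacerbation, resource-use and adverse-event tables use patients evaluable at enrolment and are unaffected. SGRQ and EQ-5D-5L are collected only at enrolment, month 6 and month 12, so re-assignment recovers almost nothing for them. Strict window limits would change nothing, as no whole day lies on a limit.

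One counterpoint: requiring form and date to agree does not secure accurate timing. Tables 20-22 accept tests from the previous 3 months, so spirometry from month 7.6 can enter as a 12-month value through a visit at month 10.6, while spirometry at month 11 on a 9-month form enters nowhere.

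**Conclusion.** The point holds as a gap in the visit definition. Under the rule as worded, a record dated in a neighbouring window is discarded even where it is that patient's only record there, and the planned tables would not show it. The printed upper limit contradicts the rule and gives different patient sets for late visits, so the two must be reconciled in any case.

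The size cannot be established from the documents. On 160 patients at month 12 it is about 0 to 2 under independent deviations (SD 0.5 to 1.0 month) and about 5 to 15 under cumulative drift (gap SD 0.5 to 0.75 month). Both models, and their SDs, are assumptions. The documents do not support a claim that a large share of late data will be lost, or that precision is threatened. Some SAP sections and tables are not in the supplied text, so a re-assignment rule there cannot be excluded, although section 3 is where it would belong.

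**What to change.** In SAP section 3, under the definition of patients who performed each follow-up visit:

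1. Assign each follow-up record to the window in which (own visit date − enrolment date)/30.4375 falls, whatever the month on its form. Apply the collected-form and symptom-data conditions to the assigned record.
2. If two records fall in one window, use the one that has the relevant assessment and lies nearest the target month.
3. Correct the upper-limit line so that each visit is tested on its own date field.
4. Report, by form month, the number of records re-assigned and the number outside all windows, for example beside Table 4.

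The cost is SAP wording and a short derivation step; no new data are needed. One small drawback is that analysis visit and form label will differ for some patients. Assignment by visit date also does not align a lung-function test done up to 3 months earlier with its nominal month.
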